Parenteral artesunate is the first line treatment for severe malaria as recommended by [WHO 2015](#). All participants will be treated with IV cipargamin or IV artesunate for at least 24 h (minimum of 2 doses of IV cipargamin and 3 doses of IV artesunate) and until oral therapy can be tolerated. IV therapy will be followed by oral antimalarial therapy as per standard treatment practice. The oral treatment is a 3-day course of Coartem to ensure complete elimination of parasites in participants.

The open label design is chosen since the dosing frequency and method of administration of test drug and comparator is not similar. Hence, blinding the treatment would require multiple placebo injections in a double dummy design which is ethically not acceptable considering the severity of the disease and need for inclusion of pediatric participants. Furthermore, the risk of bias arising out of the open-label design is minimized due to the objectivity of the primary endpoint, which is based on reduction of parasitemia.

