6.1.2 Additional study treatments

6.1.2.1 Oral medication (standard of care)

All sites will receive Coartem as standard of care for oral treatment as per local practice. Following criteria are recommended for specified timepoints when switching participant from IV therapy to oral therapy as mentioned in below [Table 6-4](#):

First timepoint to switch participant from IV therapy to oral is at 48 hour. However, if a participant is not able to tolerate oral therapy then continue with IV treatments and evaluate again at 72 hour timepoint.

Table 6-4 Criteria for switch to oral medication (standard of care)

Time	Decision criteria	Decision
0 hours	Review screening results	Start dosing with IV therapy
24 hours	Assess rescue medication criteria	Continue IV therapy (and assess rescue medication criteria for participants on IV cipargamin) (see Section 6.2.1)
48 hours (Day 3) (1 st timepoint for a switch to oral therapy)	Assess the feasibility of administering oral medication	Start Coartem, if switch criteria are met as per label. Otherwise continue IV therapy (and assess rescue medication criteria per Section 6.2.1)
72 hours (Day 4) onwards	Assess the feasibility of administering oral medication at every 24 hours	Start Coartem, if switch criteria are met as per label. Otherwise continue IV artesunate or switch to IV artesunate therapy (for participants on IV cipargamin as per Section 6.2.1). Hospitalization should be extended till the time participant has not switched to oral therapy and assessments to be repeated as Day 4 if hospitalization is required beyond Day 4 (see Table 8-1 , Table 8-2)

Intravenous artesunate can be administered to a maximum of 7 days based as per supplied labels. Most participants after switching to oral therapy will be discharged from hospital with full oral course of Coartem for 3 days. Site to instruct participant (or participant's representative) on intake of oral therapy per label.

After switching to oral therapy (Coartem), if there are efficacy or safety concerns, the participant will be administered another ACT ([Section 6.2.1](#)) as per local treatment guidance.

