Analysis of secondary endpoints related to parasite clearance dynamics

All analyses will be performed using the FAS.

Proportions of participants with ≥ 90% *P. falciparum* asexual parasite reduction from baseline at 24 and 48 hours: missing data due to intercurrent and non-intercurrent events will be handled similar to the primary efficacy endpoint (See [Section 12.4.3](#), [Section 12.4.4](#)). These 2 variables will be analyzed using the statistical methods specified in [Section 12.4.2](#), [Section 12.4.5](#) and [Section 12.4.6](#).

PRRs at 12, 24 and 48 hours: PRR is defined as the ratio of asexual parasite at baseline divided by asexual parasite at post-baseline. If the asexual parasite count at post-baseline is 0, the half value of detection limit will be used to calculate the ratio. Missing values will not be imputed. For each PRR, 2-sided 90% CIs for each treatment group and for treatment ratio between each IV cipargamin regime vs IV artesunate by cohort will be provided using an analysis of covariance (ANCOVA) model on the log scale with log baseline value as a covariate and treatment group as a factor. For all cohorts pooled, the analysis will be performed with cohort as an additional factor in the ANCOVA model.

PCT and FCT: PCT will be calculated based on uncorrected *P. falciparum* asexual parasite counts. If a participant does not experience an event (such as *P. falciparum* parasite clearance, etc.), the time to the event will be censored at the last relevant assessment (such as last *P. falciparum* parasite assessment, etc.) participants who do not have the health condition at baseline (eg, fever, etc.) will be excluded from the corresponding time to event analysis (eg., FCT, etc.). Descriptive statistics will provided using the Kaplan-Meier method and Kaplan-Meier curves will be presented by treatment and cohort. For all cohorts pooled, difference for the cipargamin regimen vs artesunate will be evaluated using a log-rank test stratified by cohort. Two-sided 90% CIs for the hazard ratio will be provided.

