*Results from Cohort 1 and Cohort 2 will be analyzed to determine the safe and efficacious exposure range and the corresponding doses (KAE dose regimen 3) for participants in Cohorts 3 to 5.

Doses for Cohort 4 will be confirmed after PK analysis from upto 6 KAE609 participants from Cohort 3 and for Cohort 5, it would be post completion of Cohort 4 .

** Cohort 5 recruitment is dependent on availability of adequate toxicology package to dose down to ≥ 6 m

KAE609 doses across the study will be adaptive depending on the safe and efficacious exposure range identified before the study (for Cohorts 1-2) and after interim assessment of Cohort 1 & 2 (for Cohorts 3-5)

Randomization is stratified within each cohort according to country and previous antimalarial therapy use to achieve the balanced treatment allocation for these stratification factors.

Patients will be admitted to the hospital on Day 1. They will remain in hospital under close supervision until they are discharged by the investigator or designee on Day 4. At the discretion of the investigator, patients may stay for additional days if needed. The patients will then be followed up at Days 6, 8, 15, 22, and 29. Visits to assess safety and efficacy will be scheduled during the follow-up period as described in the schedule of assessments tables (Table 8-1 and Table 8-2) in the protocol.

In all cohorts, patients on IV cipargamin regimens will receive once daily injection of IV cipargamin over a minimum of 2 days and a maximum of 3 days; with IV artesunate as rescue medication. Patients in the IV artesunate regimen will be administered a minimum of 3 doses during the first 2 days of treatment. There is no rescue medication for IV artesunate regimen since it is the standard of care therapy recommended by WHO; however, if the patients are not responding in first 2 days, they will be treated for longer with IV artesunate. Patients in all regimens will receive Coartem BID for 3 days following IV therapy.

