2.1.1 General definitions

Study treatment: IV Cipargamin and IV artesunate are randomized treatments. Coartem tablets (20/120 mg and 80/480 mg tablets) are used for oral therapy following the IV therapy for all patients. Coartem is not an investigational treatment and will not be presented in the treatment group name. Treatment group name will be used in statistical analyses and outputs. These treatment groups will be used as the column headers in the CSR outputs.

For example, the initial treatment groups in Cohort 1-2 will be displayed as:

- IV Cipargamin 20mg

- IV Cipargamin 40mg
- IV Artesunate

As per study design, other IV cipargamin dose levels may also be used. Treatment groups for each of the combinations will be used accordingly. For Cohorts 3 to 5, the IV Cipargamin dose level will be the equivalent dose level intended for patients ≥ 35 kg.

Baseline: The last measurement made prior to administration of the first dose of study treatment. Note: this may include measurements taken on the day of randomization (e.g. lab, ECG, vitals).

Study day: Study day will be calculated with respect to the first dose of study treatment. If a patient did not receive any dose of study treatment then the randomization date will be used as the date of first dose of study treatment. The first day of administration of study treatment (first dose) is defined as Day 1. Day -1 will be the day before Day 1. Day 0 does not exist. For some variables, assessments are collected more than once a day during first 3 days. Study day calculation for such assessments is based on the treatment start date and time.

For the assessments that are performed more than once a day: Study day = Integer (datetime of assessment – datetime of first dose of study treatment)/(60*60*24) + 1.

For assessments that are performed once for a day: Study day = date of assessment – date of first dose of study treatment + 1.

For assessments collected prior to Day 1, study day = date of assessment - date of first dose of study treatment.

Body temperature: Body temperature is measured using different routes (oral/rectal/tympanic/axillary), which will lead to variations in the readings. Therefore, all the temperature readings will be standardized with respect to tympanic equivalent as follows for the reporting purpose:

Body temperature (oral/tympanic/rectal equivalent) = Axillary temperature + 0.5°C.

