Fever Clearance time (FCT) (in patients with temperature of $\geq 37.5^{\circ}\text{C}$ axillary or $\geq 38.0^{\circ}\text{C}$ oral/tympanic/rectal) is defined as time from the first IV study medication until the first time the body temperature decreased below and remained below 37.5°C axillary or 38.0°C oral/tympanic/rectal for at least a further 24 hours,

Parasite clearance time (PCT) is defined as time from the first IV study medication until the first total and continued disappearance of asexual parasite forms which remained at least a further 48 hours.

Parasitaemia: P. falciparum asexual parasite counts are based on the local lab assessment for all cohorts and repeated using central lab assessments for Cohorts 1 and 2. Similar use of local lab readings and central lab readings will be applied to PRR, recrudescence, reinfection, and clinical success below.

Parasite detection limit for central lab: 0.1 parasite/uL will be used as detection limit or assay sensitivity limit for the parasite counts using the central lab.

Parasite detection limit for local lab: 10 parasite/uL will be used as detection limit or assay sensitivity limit for the parasite counts using the central lab.

PRR is defined as the ratio of asexual parasite at baseline divided by asexual parasite at post-baseline. If the asexual parasite count at post-baseline is 0, the detection limit will be used to calculate the ratio.

Recrudescence and reinfection

Recrudescence is defined as appearance of asexual parasites after clearance of initial infection with a genotype identical to that of parasites present at baseline. Recrudescence must be confirmed by PCR analysis.

Reinfection or new infection is defined as appearance of asexual parasites after clearance of initial infection with a genotype different from those parasites present at baseline.

Clinical success

Clinical success is a composite endpoint defined based on the following criteria.

A patient is said to have achieved the clinical success at a given timepoint if the patient did not die either during the initial hospitalization nor due to malaria post the initial hospitalization, shows absence of *P. falciparum* asexual parasites, and did not have any of the key signs or symptoms of severe malaria on that given timepoint.

Note: Deaths occurring post initial hospitalization will be evaluated by designated adjudication committee to confirm if they are related to malaria.

Key signs of Severe Malaria

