2.7.2.4 Time to event analyses

Time to event will be calculated from the time of first study medication to the date of first event if a patient experiences the event and be censored at the time of last assessment if a patient does not experience the event. Randomization date will be used in the absence of study medication date.

For the following time to event variables, the first visit with the event will be used to calculate the time if a patient experiences the event. If a patient does not experience the event, the time will be censored at the last visit assessment for the specific type of event (such as last sit assessment, etc.) with the exception of date of discontinuation (or death) for time to oral antimalarial therapy.

- Time to *P. falciparum* asexual parasite clearance (PCT) (in hours)
- Time to fever clearance (FCT) (in hours)
- Time to oral antimalarial therapy (in hours),
- Time to recover prostration (in hours) in patients who are prostrated at baseline

Descriptive statistics (mean, standard error, median, quartiles) will be presented using the Kaplan-Meier method by treatment and cohort. Kaplan-Meier curves will be provided by treatment and cohort. For all cohorts pooled, difference for the cipargamin regimen vs artesunate will be evaluated using a log-rank test stratified by cohort (Cohorts 1 and 2 pooled as one cohort). Two-sided 90% CIs for the hazard ratio will be provided.

PCT will be calculated based on *P. falciparum* asexual parasite counts. Patients without parasite clearance for whatever reason will be censored at the time of last parasite assessment. Patients who received any non-study IV antimalarial medication (including IV rescue medication) before parasite clearance will be censored at the first use of antimalarial medication.

Patients who did not have a fever at pre-dose will not be included in the analysis of FCT. Patients without fever clearance for whatever reason will be censored at the time of last temperature assessment. Patients who received any antimalarial medication (including rescue medication) before fever clearance will be censored at the first use of antimalarial medication.

Patients without switching to oral medication for whatever reason will be censored at the time of last study assessment. Patients who received any IV rescue medication will be censored at the first use of IV rescue medication.

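### The SAP censors fever clearance at any antimalarial; as worded this catches the planned Coartem, and the protocol has no such rule

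*SAP*

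**What the plan says.** FCT is a secondary endpoint. SAP 2.1.1 dates clearance from the first IV dose to the first time the temperature "decreased below and remained below 37.5°C axillary or 38.0°C oral/tympanic/rectal for at least a further 24 hours". SAP 2.7.2.4 analyses it by Kaplan-Meier per cohort and, for pooled cohorts, by a stratified log-rank test and a hazard ratio with a 90% confidence interval.

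The censoring sentence for FCT reads: "Patients who received any antimalarial medication (including rescue medication) before fever clearance will be censored at the first use of antimalarial medication". The rule just before it, for parasite clearance time (PCT), is narrower and applies to "any non-study IV antimalarial medication (including IV rescue medication) before parasite clearance". The rule just after it, for time to oral therapy, is limited to IV rescue.

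Coartem is part of the plan in every arm: "Patients in all regimens will receive Coartem BID for 3 days following IV therapy" (SAP 1.1). On timing, Protocol 6.1.2.1 says: "First timepoint to switch participant from IV therapy to oral is at 48 hour". Protocol 4.1 describes it as an antimalarial: "IV therapy will be followed by oral antimalarial therapy as per standard treatment practice. The oral treatment is a 3-day course of Coartem". SAP 2.1.1 adds: "Coartem is not an investigational treatment and will not be presented in the treatment group name".

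Protocol 12.5.1 treats PCT and FCT together. For a participant without the event, "the time to the event will be censored at the last relevant assessment". It has no censoring at antimalarial use. SAP Section 4, on changes to protocol-specified analyses, says there are none.

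**The concern.** Taken at its word, the FCT rule ends follow-up for anyone still febrile when scheduled oral treatment begins. A fever that resolves after the switch is then not an event. What would be at stake is the later part of the FCT curve, the upper quartile that the SAP promises, and the number of events behind the log-rank test and hazard ratio. Who remains at risk after 48 h also matters: they are the participants not yet able to take oral treatment, and they may well recover more slowly. A rule with these effects appears in the SAP but not in the protocol, and is not declared as a change.

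**Working it through.** The documents state no FCT rate, event count or power, so there is no figure to reproduce. The check is mainly textual, followed by an illustration on stated assumptions.

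**1. The rules side by side**

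| Rule | Drugs that censor | Does scheduled Coartem censor, as worded? |
|---|---|---|
| PCT, SAP 2.7.2.4 | Non-study, IV (including IV rescue) | No: it is oral |
| Time to oral therapy, SAP 2.7.2.4 | IV rescue | No |
| FCT, SAP 2.7.2.4 | Any antimalarial | Yes |
| PCT and FCT, Protocol 12.5.1 | None | No |

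The same SAP section names the switch to Coartem as time to oral antimalarial therapy, so the SAP itself classes Coartem as an antimalarial. Table 5-11 (non-study antimalarials) omits the artemether-lumefantrine combination, but the FCT rule neither cites that table nor uses its term.

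**2. The sentence cannot be programmed as it stands.** Any antimalarial also covers the randomized IV drug at time 0, which would censor everyone at zero. Some qualifier is needed, and the text does not say which.

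**3. The confirmation window.** Clearance needs a further 24 h below the threshold. A first afebrile reading between 24 h and 48 h is confirmed only after 48 h, possibly after Coartem has started. The SAP does not say whether that counts as clearance before the antimalarial.

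**4. Share of clearances after 48 h.** Assume exponential FCT with median m, everyone febrile at baseline, and everyone switching at 48 h. The share is 2^(−48/m). The count uses the planned 116 per pooled arm; it is an upper figure, because participants without fever pre-dose are excluded.

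| Assumed median m (h) | 2^(−48/m) | Of 116 |
|---|---|---|
| 12 | 6% | 7 |
| 18 | 16% | 18 |
| 24 | 25% | 29 |
| 36 | 40% | 46 |
| 48 | 50% | 58 |

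**5. Effect on the Kaplan-Meier estimate.** This was a simulation of 200,000 participants on the scheduled temperature visits, with exponential times (scale set by a 36 h median) divided by a gamma frailty (shape 2, mean 1).

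| Cumulative clearance | 48 h | 72 h | 120 h |
|---|---|---|---|
| True | 53% | 65% | 78% |
| Rule as worded, all switch at 48 h | 53% | 53% | 53% |
| Rule as worded, random 80% switch at 48 h | 53% | 65% | 65% |
| Rule as worded, faster recoverers switch first | 53% | 61% | 61% |

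Nothing changes up to 48 h. At 72 h there is bias only when switching is related to recovery (61% against 65%), or no estimate beyond 48 h when all switch. In every case the curve stops rising once everyone has switched.

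**6. Effect on information.** Schoenfeld's approximation, two-sided alpha 0.10, assumed hazard ratio 1.4: power = Φ(ln(1.4) × √D / 2 − 1.645), where D is the number of events. With all 2 × 116 = 232 clearances counted, power is 82%. Counting only those by 48 h, D = 232 × (1 − 2^(−48/m)):

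- m = 24 h: D = 174, power 72%
- m = 36 h: D = 140, power 64%
- m = 48 h: D = 116, power 57%

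**The case against.** The strongest reply is that the literal reading proves too much. If the randomized drug must be exempted by common sense, the natural exemption covers the whole planned regimen, Coartem included. The documents lend this some support: SAP 2.1.1 describes Coartem under its study treatment definition, the protocol glossary counts non-investigational products as study treatment, and Table 5-11 leaves the combination out. Dropping the IV limit may also have been deliberate, because Protocol 6.2.1 allows an oral rescue ACT after Coartem. That probably is the intent. But it remains an inference. No sentence exempts Coartem, and a programmer who applied the rule to every antimalarial given after the first dose would be following the text.

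A second reply is that ending the FCT comparison at the oral switch is defensible, since both arms then receive the same drug. That is arguable, but it would be a different question from the one Protocol 12.5.1 sets, and it would need to be stated.

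Other parts of the reply stand. The switch criterion in Protocol 6.1.2.1 is whether oral medication is feasible, not fever or recovery as such, so informative censoring is plausible but not documented. Censored participants still contribute time at risk until the switch, and 48 h is only the earliest switch. A reader might therefore infer that all late clearance is ignored; the documents do not support that, because clearances in participants still on randomized IV treatment would count.

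**Conclusion.** The rule is wrong as written, in a limited way. The FCT sentence needs a qualifier that it lacks, and it departs from Protocol 12.5.1 without being declared. If it is applied to Coartem, clearances after the oral switch drop out as events, with the effects on the later curve, the upper quartile and the between-arm comparison shown above.

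The size is unknown. The medians, frailty, switching patterns, hazard ratio and universal baseline fever used in the illustration are assumptions, and none comes from the documents. A median FCT below 48 h would be unaffected if the rule is applied only to Coartem.

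A reader might go further and infer that the trial's efficacy conclusions are at risk, or that one arm is favoured. The documents do not support either. FCT is secondary with no pre-specified hypothesis, the primary and key secondary endpoints do not use this rule, and nothing given allows the direction of any bias between arms to be worked out.

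**What to change.** Reword the FCT sentence in SAP 2.7.2.4 so that only non-study and rescue antimalarials, IV or oral, censor. State in the same place that the randomized IV drug and scheduled Coartem do not censor. If Table 5-11 is cited to define non-study drugs, note that it lists artesunate, which is also the randomized control. Add a clause saying how a first afebrile reading before the switch, confirmed after it, is classified.

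Censoring at rescue is still more than Protocol 12.5.1 provides, so list that remaining departure in SAP Section 4.

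The cost is two or three sentences in the SAP and one entry in Section 4, with a matching change to the FCT derivation. No new data are needed, and it should be settled before database lock.

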PCE slope half-life: PCE slope half-life will be calculated for each participant using the WWARN (World Wide Antimalarial Resistance Network) Parasite Clearance Estimator as described in [Flegg et al 2011](#). 2-sided 90% CIs for each treatment group and for treatment ratio between each IV cipargamin regime vs IV artesunate by cohort will be provided using an analysis of covariance (ANCOVA) model on the log scale with log baseline value as a covariate and treatment group as a factor. For all cohorts pooled, the analysis will be performed with cohort as an additional factor in the ANCOVA model.

Incidence of recrudescence and reinfection during the study

Reinfection is defined as appearance of asexual parasites after clearance of initial infection with a genotype different from those parasites present at baseline.

Recrudescence is defined as appearance of asexual parasites after clearance of initial infection with a genotype identical to that of parasites present at baseline. Recrudescence must be confirmed by PCR analysis.

Incidence rates of recrudescence and reinfection at Study Day 29 will be estimated by Kaplan-Meier method based on the subset of FAS participants who have clearance of initial infection by Study Day 7. Time to recrudescence/reinfection will be calculated from the time of first IV study medication to the date of first event if a participant experience the event and be censored at the time of last parasite assessment if a participant does not experience the event.

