Patients who did not have a prostration at pre-dose will not be included in the analysis of time to recover prostration. Patients who do not recover prostration after the IV treatment for whatever reason will be censored at the last study assessment.

Above analysis will be based on FAS.

Tail of KM plots: Since the tail of KM plots after the day of last planned assessment is not reliable due to small numbers of patients at risk, the time to event will be reset to planned last day, i.e. Day 29, regardless of censoring. This principle will be used for relevant tables using the KM method.

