2.7.2.4.1 Time to event analysis for Recrudescence

Recrudescence is defined as appearance of asexual parasites after clearance of initial infection with a genotype identical to that of parasites present at baseline. Recrudescence must be confirmed by PCR analysis.

Incidence rates of recrudescence up to Day 29 will be estimated by the Kaplan-Meier method based on the subset of FAS patients who have clearance of initial infection by Day 7. Descriptive statistics (mean, standard error, median, quartiles) will be presented using the Kaplan-Meier method by treatment and cohort. Kaplan-Meier curves will be provided by treatment and cohort. For all cohorts pooled, difference for the cipargamin regimen vs artesunate will be evaluated using a log-rank test stratified by cohort (Cohorts 1 and 2 pooled as one cohort). Two-sided 90% CIs for the hazard ratio will be provided.

Time to event (recrudescence) will be calculated from the time of first study medication to the date of first event if a patient experience the event and be censored at the time of last parasite assessment if a patient does not experience the event. Reappearance of the parasites but with missing PCR data will be considered as censored at the time of reappearance of parasites.

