2.7.2.4.2 Time to event analysis for reinfection

Reinfection is defined as appearance of asexual parasites after clearance of initial infection with a genotype different from those parasites present at baseline. Reinfection must be confirmed by PCR analysis.

Incidence rates of reinfection at Day 29 will be estimated by the Kaplan-Meier method based on the subset of FAS patients who have clearance of initial infection by Day 7. Descriptive statistics (mean, standard error, median, quartiles) will be presented using the Kaplan-Meier method by treatment and cohort. Kaplan-Meier curves will be provided by treatment and cohort. For all cohorts pooled, difference for the cipargamin regimen vs artesunate will be evaluated using a log-rank test stratified by cohort (Cohorts 1 and 2 pooled as one cohort). Two-sided 90% CIs for the hazard ratio will be provided.

Time to event (reinfection) will be calculated from the time of first study medication to the date of first event if a patient experiences the event and be censored at the time of last parasite assessment if a patient does not experience the event. Reappearance of the parasites but with missing PCR data will be considered as censored at the time of reappearance of parasites.

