Table 5-9 Analysis visit windows based on study day and time

Target visit	Target timepoint	Blood smear	PK (Cohorts 1 to 3)	PK (Cohorts 4-5)	Neurological/severe malaria assessment/ body temperature/blood pressure/pulse	Blood chemistry/hematology Point of Care device	Urinalysis
Baseline	0 hrs	up to 0 hrs	up to 0 hrs	NA	up to 0 hrs	up to 0 hrs	up to 0 hrs
Day 1	2 m	NA	>0 – 6m	>0 – 31 min	NA	NA	NA
	10 m	NA	>6m – 35 m	NA	NA	NA	NA
	30 m	NA	NA	NA	>0 – 3.25 hrs ¹	NA	NA
	1 hrs	>0 - 1.5 hrs	>35 m- 2.5 hrs	>31 min- 12.5 hrs	NA	NA	NA
	2 hrs	>1.5 – 3 hrs	NA	NA	NA	NA	NA
	4 hrs	>3 – 5 hrs	>2.5 – 8 hrs	NA	NA	NA	NA
	6 hrs	>5 - 9 hrs	NA	NA	>3.25-9 hrs	> 0 – 9 hrs ²	NA
	12 hrs	>9 - 15 hrs	>8- 18 hrs	NA	>9 - 15 hrs	>9 – 18 hrs	NA
	18 hrs	>15 - 21 hrs	NA	NA	>15 - 21 hrs	NA	NA
Day 2	24 hrs	>21 – 27 hrs	>18 – 24 hrs 1 min	>12.5 hrs – 36 hrs	>21 – 30 hrs	>18 -30 hrs	>0 – 30 hrs
	24 hrs 2 min	NA	>24 hrs 1 min-24 hrs 31 min	NA	NA	NA	NA
	25 hrs	NA	>24 hrs 31 min– 30.5 hrs	NA	NA	NA	NA
	30 hrs	>27 – 33 hrs	NA	NA	NA	NA	NA
	36 hrs	>33 – 39 hrs	>30.5 –42 hrs	NA	>30 – 42 hrs	>30 – 42 hrs	>30 -42 hrs

Target visit	Target timepoint	Blood smear	PK (Cohorts 1 to 3)	PK (Cohorts 4-5)	Neurological/severe malaria assessment/ body temperature/blood pressure/pulse	Blood chemistry/hematology Point of Care device	Urinalysis
	42 hrs	>39- 45 hrs	NA	NA	NA	NA	NA
Day 3 e	48 hrs	>45 – 60 hrs	m>42 – 48 hrs 1 min	>36 hrs	>42 -60 hrs	>42 -60 hrs	>42 – 60 hrs
	48 hrs 2 min	NA	>48 hrs 1 min – 48 hrs 31 min	NA	NA	NA	NA
	49 hrs	NA	>48 hrs 31 min – 54.5 hrs	NA	NA	NA	NA
	60 hrs	NA	>54.5 – 66 hrs	NA	NA	NA	NA
Day 4	72 hrs	>60 hrs to Day 5	>66 – 96 hrs	NA	>60 hrs to Day 5	>60 hrs to Day 5	>60 hrs to Day 5
Day 6	120 hrs	Day 6 – 7	>96 hrs – 144 hrs	NA	Day 6 – 7	Day 6 – 7	Day 6 -7
Day 8	168 hrs	Day 8 - 11	>144 hrs	NA	Day 8 - 11	Day 8 – 11	Day 8 -11
Day 15	336 hrs	Day 12 - 18	NA	NA	Day 12 - 18	Day 12 – 18	Day 12 - 18
Day 22	504 hrs	Day 19 - 25	NA	NA	Day 19 - 25	Day 19 - 25	Day 19 - 25
Day 29	672 hrs	Day 26 and above	NA	NA	Day 26 and above	Day 26 and above	Day 26 and above

¹ for body temperature and vital signs; ² for Point of Care device

Table 5-10 Rules for flagging variables

Timing of measurement	Type of data	Rule
Baseline	All data	The last measurement made prior to administration of the first dose of study treatment – note this may include measurements taken on the day of randomization. If a patient did not receive any dose of study treatment then the randomization date will be used.

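### The SAP's Day 29 tail reset works on one side only: late final visits are pulled back to Day 29 while Day 27-28 completers stay censored early, so the Kaplan-Meier incidence of recrudescence and reinfection is overstated

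*SAP*

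**What the plan says.** Both endpoints are Kaplan-Meier estimates in the FAS patients whose initial infection had cleared by Day 7. SAP 2.7.2.4.1: "Incidence rates of recrudescence up to Day 29 will be estimated by the Kaplan-Meier method". SAP 2.7.2.4.2: "Incidence rates of reinfection at Day 29 will be estimated by the Kaplan-Meier method".

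Times are actual times. In SAP 2.7.2.4.1 the time "will be calculated from the time of first study medication to the date of first event", and event-free patients are "censored at the time of last parasite assessment if a patient does not experience the event". SAP 2.7.2.4.2 repeats this for reinfection. Protocol 12.5.1 has the same censoring rule ("be censored at the time of last parasite assessment if a participant does not experience the event") but no rule for the tail of the curve.

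The last scheduled smear is at Day 29±2, so Days 27 to 31 (Protocol Tables 8-1 and 8-2). The one before it is at Day 22±2.

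Under its paragraph on the tail of the plots, SAP 2.7.2.4 says "the time to event will be reset to planned last day, i.e. Day 29, regardless of censoring", and extends this to the relevant Kaplan-Meier tables. Its reason is that few patients are at risk after the last planned assessment day.

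SAP Table 5-9 maps smears from "Day 26 and above" to the Day 29 visit. However, SAP 5.2.4 states the use of mapped visits for by-visit analyses only, not for Kaplan-Meier times.

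**The concern.** A patient seen event-free on Day 27 has completed the study (Protocol 9.2), yet is censored two days before the time point at which incidence is read. A patient seen on Day 31 has attended the same nominal visit, but is moved back and counted at Day 29. After Day 22 the next scheduled smear is the final one, so infections arising since then are mostly found there. The reset brings in the late attenders' events but does not keep the early attenders' event-free follow-up in the denominator.

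The proportions with recrudescence and reinfection by Day 29 are listed secondary endpoints (Protocol Table 2-1, SAP Table 1-1). The absolute incidence in each arm is the reported result, and part of it would depend on which day patients returned to the clinic.

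**Working it through.** The plan states no incidence, event count or precision for these endpoints, so there is no figure to reproduce. The product-limit estimate can be written out directly.

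**From the documents:** actual event and censoring times; last visit on Days 27-31; times after Day 29 set to Day 29; Day 27-28 times left alone.

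**Assumed, because the documents do not give them:**
- p0: incidence found before the last visit.
- q: chance of a first positive smear at the last visit among those still event-free, the same on every visit day.
- w27, w28, w29: shares of last visits on those days.
- No dropout.

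**Formulas for S, the event-free proportion at Day 29:**
- Target: S = (1 − p0)(1 − q)
- SAP as written: S = (1 − p0)(1 − w27·q)(1 − w28·q/(1 − w27))(1 − q)
- Actual dates, no reset: as above, with the last factor replaced by (1 − w29·q/(1 − w27 − w28))

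The SAP version has the whole target in it, multiplied by two further factors below 1. Reported incidence therefore exceeds the target whenever q > 0 and some last visits fall on Day 27 or 28.

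**True 9%, one third found at the last visit.** p0 = 0.06, q = 0.03/0.94 = 0.0319, target S = 0.94 × 0.9681 = 0.91.

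| Attendance, Days 27/28/29/30/31 (%) | S, SAP as written | Reported incidence |
|---|---|---|
| 5/5/80/5/5 | 0.91 × 0.99840 × 0.99832 = 0.9070 | 9.3% |
| 10/10/60/10/10 | 0.91 × 0.99681 × 0.99645 = 0.9039 | 9.6% |
| 20 on each day | 0.91 × 0.99362 × 0.99202 = 0.8970 | 10.3% |

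**True 9%, 5 of the 9 points found at the last visit, uniform attendance.** p0 = 0.04, q = 0.05/0.96 = 0.0521.
- SAP as written: 0.91 × 0.98958 × 0.98698 = 0.8888, so 11.1%.
- Actual dates, no reset: 0.96 × 0.98958 × 0.98698 × (1 − 0.2q/0.6) = 0.9214, so 7.9%.
- All last-visit times set to Day 29: 0.96 × (1 − 0.0521) = 0.91, so 9.0%.

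The second line locates the cause. With a symmetric window and actual dates only, the estimate is too low, because Day 30-31 events fall after Day 29. The reset turns this into an overstatement.

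**Simulation check.** Constant hazard from Day 8, 107 per group (the evaluable number in SAP 3.2), smears at 15±1, 22±2 and 29±2, 1,000 runs, true Day 29 incidence 10%. With scheduled detection only, the SAP rule gave 11.0% (attendance 10/20/40/20/10), 11.6% (uniform) and 11.3% (25/25/50/0/0). With half of events caught at unscheduled visits it gave 10.8% to 11.1%. Setting all last-visit times to Day 29 gave 9.6% to 10.1% across the same settings.

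Days 15 and 22 do not have this problem, because event-free patients remain at risk after those visits.

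**The case against.** The strongest reply is that the operative clause carries no condition limiting it to times later than Day 29. If the sponsor means every final visit to be set to Day 29, the problem disappears. That stands as a possible intention. But the only reason given is the unreliable tail after the last planned day, and Day 27-28 times are not in that tail. A programmer could implement either reading, and the two give different results.

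The second reply concerns size. Some events will be found at Days 15 and 22, and participants are told to contact the investigator if symptoms re-emerge (Protocol section 3), with a blood film at unscheduled visits. Both shrink the last-visit component and so the bias. This stands, and the range below allows for it.

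Third, the SAP pre-specifies no hypotheses for these endpoints (2.7.2), and both arms follow the same visit schedule. This also stands, and limits the consequence to the reported incidence.

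Several stronger inferences do not hold:
- That actual-date timing is itself the fault, or that the protocol shares it. Protocol 12.5.1 has no reset, and with a symmetric window its rule would slightly understate incidence.
- That the endpoint is inflated by 45% or 21%. Those ratios (0.2q + 0.25q + q = 1.45q for uniform attendance; 0.1q + 0.11q + q = 1.21q for 60% on Day 29) describe only the last-visit component.
- That events are counted twice. Each event enters once; the last-visit hazard is estimated on successive days from shrinking risk sets.
- That the treatment comparison is biased. That would need visit timing to differ between arms, and nothing in the documents suggests it.

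**Conclusion.** As written, the SAP's one-sided reset overstates the Day 29 Kaplan-Meier incidence whenever some final visits fall on Day 27-28 and events are still found at final visits on or after Day 29. Direction and mechanism follow from the text; the size does not, because it rests on assumed event rates and attendance. For a true 9%, the cases worked through run from about 0.3 points too high (80% attend on Day 29, one third of events at the last visit) to about 2.1 points too high (uniform attendance, 5 of the 9 points at the last visit). If everyone attends on Day 29 there is no bias.

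The error affects the absolute incidence by arm of a stated secondary endpoint. The log-rank test and hazard ratio should be little affected if visit timing is similar between arms. The primary and key secondary analyses are untouched. It is worth correcting before database lock, but does not threaten the trial's main conclusions.

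**What to change.** In SAP 2.7.2.4 to 2.7.2.4.2, state that for recrudescence and reinfection the event or censoring time of every final assessment in the Day 29 smear window of Table 5-9 ("Day 26 and above") is set to Day 29, whether it falls before or after the planned day. Patients who leave before that window stay censored at their last smear.

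This needs one sentence and a small programming change, and no new data. It also settles how the tail rule is to be read. The cost is that last-visit times become nominal days. The rule reproduces the proportion observed at the final visit, so an infection arising between a Day 27 visit and Day 29 is not seen. In the simulation with half of final visits on Day 27-28 and none after Day 29, that gave 9.6% against a true 10%, a smaller error than the 11.3% under the current rule.
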